#### 9.1.2 Impact of Study Treatment

The impact the event had on the study treatment will be assessed as either: none, study treatment interrupted, study treatment discontinued, or not applicable. The "not applicable" assessment will

be used only when the subject is no longer in the treatment phase of the protocol, or if the outcome of the event was “death”.

### 9.1.3 DAIDS AE Grade (Severity) Assessment

The Investigator will carefully evaluate the comments of each subject and the response to treatment in order to judge the true nature and severity of the AE. The question of the relationship of AEs to study drug should be determined by the Investigator after thorough consideration of all available facts. To assess severity, the Investigator will use the DAIDS AE grading table (for adverse events as well as any injection site reactions refer to [Section 17.2](#) and [Section 17.3](#)).

The general guidelines for assessing the AE grade appear below. Full guidelines may be obtained at [http://rsc.tech-res.com/Document/safetyandpharmacovigilance/DAIDS\\_AE\\_Grading\\_Table\\_v2\\_NOV2014.pdf](http://rsc.tech-res.com/Document/safetyandpharmacovigilance/DAIDS_AE_Grading_Table_v2_NOV2014.pdf).

**Table 9-1: DAIDS AE Grading General Guidelines**

Grade	Description
Grade 1	indicates a mild event
Grade 2	indicates a moderate event
Grade 3	indicates a severe event
Grade 4	indicates a potentially life-threatening event
Grade 5	Death related to AE.

DAIDS AE Grading Table Version 2.0- November 2014

### 9.1.4 Causality Assessment

Adverse events will be assigned a relationship (causality) to the study treatment. The Principal Investigator (PI) must review each AE and make the determination of relationship of the event to the study treatment. Relationship of AEs to study treatment will be classified as follows:

- 1. Definitely related:** This category applies to those AEs that the Investigator feels are incontrovertibly related to the study treatment. An AE may be assigned an attribution of definitely related if or when it meets all of the following criteria: (1) it follows a reasonable temporal sequence from administration of the study treatment; (2) it could not be reasonably explained by the known characteristics of the subject’s clinical state, environmental or toxic factors, or other modes of therapy administered to the subject; (3) it follows a known response pattern to treatment with the study treatment.
- 2. Probably related:** This category applies to those AEs which, after careful medical consideration at the time they are evaluated, are felt with a high degree of certainty to be related to the study treatment. An AE may be considered probable if or when (must have

three): (1) it follows a reasonable temporal sequence from administration of the study treatment. (2) It could not readily have been produced by subject's clinical state, environmental or toxic factors, or other therapies administered to the subject. (3) Disappears or is decreased upon discontinuation of the study treatment. (4) It follows a known response pattern to treatment with the study treatment.

3. **Possibly related:** This category applies to those AEs which, after careful medical consideration at the time they are evaluated, are judged unlikely but cannot be ruled out with certainty to the study treatment. An AE may be considered possible if or when (must have two): (1) it follows a reasonable temporal sequence from administration of the study treatment. (2) It could not readily have been produced by subject's clinical state, environmental or toxic factors, or other therapies administered to the subject. (3) Disappears or is decreased upon discontinuation of the study treatment. (4) It follows a known response pattern to treatment with the study treatment.
4. **Remotely related:** In general this category can be considered applicable to those AEs which, after careful medical consideration at the time they are evaluated, are judged likely to be unrelated to the study treatment. An AE may be considered unlikely if or when (must have two): (1) it does not follow a reasonable temporal sequence from administration of the study treatment. (2) It could not readily have been produced by subject's clinical state, environmental or toxic factors, or other therapies administered to the subject. (3) Disappears or is decreased upon discontinuation of the study treatment. (4) It does not follow a known response pattern to treatment with the study treatment.
5. **Unrelated:** This category applies to those AEs which, after careful consideration at the time they are evaluated, are clearly and incontrovertibly due to extraneous causes (disease, environment, etc.) and determined with certainty to have no relationship to the study treatment.

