## (b) Subjects who experience Virologic Failure

## • Short-Term Follow-Up Visits

Procedure/Assessments	Follow-Up Visit -1	Follow-Up Visit -2	Follow-Up Visit -3 
	VF-FU1	VF-FU2	VF-FU3
Window Period	4 weeks (±7 days) after VF visit	8 weeks (±7 days) after VF visit	12 weeks (±7 days) after VF visit
Physical Examination	X 	X 	X 
Vital Signs	X	X	X
Plasma HIV-1 RNA level	X	X	X
TruCount T assay	X	X	X
Anti-idiotypic Antibodies to PRO 140	X		
Re-initiate combination Antiretroviral Therapy	X	X	X
Adverse Events	X	X	X
Concomitant Medications	X	X	X

[1] Subject will be followed up every 4 weeks until viral suppression is achieved (i.e., plasma HIV-1 RNA levels decline to < 50 copies/mL). Subject will undergo additional follow-up visits every 4 weeks beyond VF-FU3 visit (up to a maximum of 6 months after re-initiation of combination antiviral therapy), if viral suppression is not achieved at the end of VF-FU3 visit.

[2] Symptom-directed physical examination

- Long-Term Follow-Up Visits

Procedure/Assessments	Long-Term Follow-Up Visit -1	Long-Term Follow-Up Visit -2
	VF-6mFU	VF-12mFU
Window Period	6 months ( $\pm 1$ month) after VF visit	12 months ( $\pm 1$ month) after VF visit
Adverse Events 	X	X
Assessment of cART changes 	X	X
Plasma HIV-1 RNA level	X	X
TruCount T assay	X	X
Trofile ® DNA or RNA Assay 	X	X
PhenoSense ® Entry Assay 	X	X
HIV-1 Drug Resistance Assay 	X	X

[1] Only SAEs and any AE that is considered possibly or probably or definitely related to the IP by the investigator will be captured during the long term follow up phase.

[2] Any changes to the combination antiretroviral regimen since the viral re-suppression is achieved.

[3] Monogram Biosciences Trofile® DNA or RNA (or both) assay will be performed depending on last known HIV-1 RNA levels.

[4] Monogram Biosciences HIV-1 PhenoSense® Entry assay with AMD3100 (X4 inhibitor drug), Maraviroc and PRO 140 (R5 inhibitor drugs).

[5] Monogram Biosciences GenoSure Archive Assay or PhenoSense® GT (and PhenoSense Integrase and GeneSeq Integrase testing, if applicable), will be performed depending on last known HIV-RNA levels.

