8.2.1.1 Adverse Events

Adverse events will be coded using Medical Dictionary for Regulatory Activities (MedDRA). TEAEs are defined as events with an onset on or after the first treatment. TEAEs will be summarized by treatment group, System Organ Class (SOC), and preferred term (PT). The following TEAE summaries will be provided:

- Overall (*i.e.*, regardless of severity or relationship to treatment)
- By severity grade (mild, moderate, severe, life threatening or death for SAEs)
- By relationship to study treatment (definitely related, probably related, possibly related, remotely related or unrelated)

In addition, separate summaries of SAEs, and AEs resulting in discontinuation of study treatment will be presented.

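### Two of the four criteria for a remotely related adverse event are the ones that support causation elsewhere, so the remote and possible categories overlap and leave gaps

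*Protocol*

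**What the plan says.** Protocol 9.1.4 grades causality in five categories. Four of them carry a list of criteria.

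- **Definite** needs all three of its criteria: an event is "definitely related if or when it meets all of the following criteria: (1) it follows a reasonable temporal sequence from administration of the study treatment"; it has no other reasonable explanation in the patient's condition, surroundings or other therapy; and "3) it follows a known response pattern to treatment with the study treatment". Improvement off drug is not on this list.
- **Probable** needs three of four: plausible timing, no ready alternative cause, improvement off drug, known response pattern.
- **Possible** uses the same four and needs two: "An AE may be considered possible if or when (must have two".
- **Remote** also needs two of four. Its lead-in describes events thought likely not to be due to study treatment. Criterion (1) is that the timing is not plausible. Criterion (2) is that the event could not readily have come from other causes. The last two read "3) Disappears or is decreased upon discontinuation of the study treatment. (4) It does not follow a known response pattern".

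The unrelated category has a description but no criteria list. Nothing in 9.1.4 says which category applies when more than one list is met.

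The rating is used downstream. SAP 8.2.1.1 summarises treatment-emergent events "By relationship to study treatment (definitely related, probably related, possibly related, remotely related or unrelated", as does Protocol 8.7.5.1 in outline. For the long-term visits of virologic-failure subjects, Protocol Table 4-3 says "Only SAEs and any AE that is considered possibly or probably or definitely related to the IP by the investigator will be captured". Protocol 4.4.1.2 and 9.1.1 repeat this.

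**The concern.** Criteria (2) and (3) of the remote list are worded as in the probable and possible lists. A fact that supports causation in items 2 and 3 is therefore used in item 4 to support its absence, against item 4's own lead-in. It looks like a copied list in which only two of four clauses were negated.

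Two things are at stake. Investigators applying the written criteria at up to 60 sites can code the same event differently, which blurs the table by relationship. And in long-term follow-up the line between possible and remote decides whether a non-serious event is captured at all.

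**Working it through.** The plan gives no figure to reproduce; this is a check of the classification logic.

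**Inputs** (Protocol 9.1.4), each 1 for yes and 0 for no: T = plausible timing; N = no ready alternative cause; D = improves off drug; K = known response pattern. The slightly different wordings of N in the definite list and the other lists are treated as one fact.

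**Rules as written**
- Definite: T = N = K = 1, D free. Patterns: 2.
- Probable: T + N + D + K ≥ 3. Patterns: 4 + 1 = 5.
- Possible: T + N + D + K ≥ 2. Patterns: 6 + 4 + 1 = 11.
- Remote: (1 − T) + N + D + (1 − K) ≥ 2. Patterns: 6 + 4 + 1 = 11.

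**All 16 patterns, named by the facts that are present**

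| Lists met | Patterns | Count |
|---|---|---|
| Possible and remote | TNDK, TND, NDK, TN, TD, ND, NK, DK | 8 |
| Possible, not remote | TNK, TDK, TK | 3 |
| Remote, not possible | N, D, none | 3 |
| Neither | T, K | 2 |

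The total is 8 + 3 + 3 + 2 = 16. Remote therefore overlaps 8 of 11 possible patterns, 3 of 5 probable (TNDK, TND, NDK) and 1 of 2 definite (TNDK). The last needs improvement off drug: TNK meets only one remote criterion, N.

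**Without D.** In long-term follow-up most subjects have stopped PRO 140, so an event that starts then cannot ordinarily improve on stopping it. With D = 0 the possible patterns are TNK, TN, TK and NK. Remote is met by TN (through N and not-K) and by NK (through not-T and N): 2 of 4. The single definite pattern and the single probable pattern, both TNK, do not meet remote.

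**Reversing criteria (2) and (3).** Remote becomes (1 − T) + (1 − N) + (1 − D) + (1 − K) ≥ 2, that is, at most two favouring facts: 6 + 4 + 1 = 11 patterns. Overlap with definite and probable falls to 0. Overlap with possible falls from 8 to the 6 patterns with exactly two favouring facts. Patterns that fit neither fall from 2 to 0.

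**Adding a rule that the highest category met applies.** The 16 patterns divide into 2 definite, 3 probable, 6 possible and 5 remote, with no overlap and no gap. Requiring three criteria for remote gives the same possible/remote split: at most one favouring fact, 4 + 1 = 5 patterns, against 11 with at least two.

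**The case against.** The best defence is that the lists are not free-standing. Each category opens with a judgement, and the criteria only say that an event may be considered to belong there. A reader might infer from the TNDK pattern that one event would be rated both definitely and remotely related. The documents do not support that: the definite category is for events the investigator holds to be beyond dispute drug-related, the remote one for events thought likely not to be. An event can meet both lists, but hardly both lead-ins.

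That defence is weak between possible and remote. Item 3 speaks of events judged unlikely to be related but not ruled out, and item 4 also calls its events unlikely. There the criteria have to separate the categories.

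A second defence is that definite, probable and possible already nest, so the scale works only if the highest category met is assigned. On that reading no overlapping event is downgraded, and remote is left with three patterns (N, D, none). But the rule is not written, and even with it the T-only and K-only patterns meet no list.

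Third, the harm is bounded. Protocol 9.1.1 collects all adverse events whatever their causality up to the final visit or, after virologic failure, until re-suppression. The filter touches only non-serious events in long-term follow-up of virologic-failure subjects. The primary safety outcomes (SAP 3.1.1) are not defined by causality, SAP 8.2.1.1 also tabulates events regardless of relationship, and SAP 7.3 and 7.4 plan no inference. All of this stands and limits the weight of the point.

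**Conclusion.** The remote list contradicts its own lead-in, and the point holds as a wording error with modest but real consequences: inconsistent coding in the relationship table, and possible non-capture of non-serious events at the long-term visits of virologic-failure subjects. Even when improvement off drug cannot occur, 2 of 4 possible patterns still meet the remote list.

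Two further inferences should be resisted. A reader might conclude that drug-related events are understated. The documents show no direction: an overlapping event can be rated up as well as down, the T-only and K-only events that fail the remote list might be rated possible, and nothing shows that misrating has happened. A reader might also take 8 of 11 as a share of events. It counts logical patterns with equal weight and says nothing about how often each occurs.

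The counts assume that each criterion is a yes/no fact, that N means the same in every list, and that the lists are read without their lead-ins.

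**What to change.** In Protocol 9.1.4 item 4, reverse criterion (2), so that the event could readily have come from other causes, and criterion (3), so that it does not disappear or lessen when study treatment stops. Then add one sentence to 9.1.4: where more than one list is met, the highest category whose criteria are met is assigned. Requiring three criteria instead of two for remote would settle the remaining six possible/remote overlaps equally well; only one of the two is needed.

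Send sites a memo. Before the relationship tables are produced, have investigators re-check ratings at the possible/remote boundary in both directions, so that the review does not itself push ratings one way.

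The cost is two reversed clauses, one added sentence, the memo and the query work. The re-check cannot recover non-serious long-term events that were never captured, and the study report should say so.

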### 9.1.5 Treatment Given as a Result of the Event

The event impact in terms of treatment provided will be as either: none, medication administered, non-medication therapy administered, surgery, or other (with a specification).

### 9.1.6 Outcome Assessment

The outcome of the event will be assessed as either: resolved, resolved with sequelae, ongoing, or death. Only one AE per subject is allowed to have an outcome assessment as "death." If there are multiple causes of death for a given subject, only the primary cause of death will have an outcome of death.

### 9.1.7 Expected / Anticipated Adverse Events

The most common potential study drug-related adverse reaction reported is mild headache. Other adverse events likely to be related to the drug include mild to moderate diarrhea, nausea, and fatigue.

### 9.1.8 SC Injection-related Events

SC and IV injections of concentrated protein materials can be associated with injection-related AEs that impact the ability to safely and successfully deliver the drug. Local injection-site reactions may include pain/discomfort, induration, erythema, nodules/cysts, pruritus, ecchymosis, etc. For SC injections, bleeding, absorption of the drug, leakage of drug, and induration at the local injection site can be additional complications. Other AEs that are common to monoclonal antibody-based therapies are chills, headache, backache, malaise, fever, pruritus, rash, nausea, tingling, and hypertension.

SC injection-related events will be monitored according to the guidelines provided in [Section 17.2](#) (Division of AIDS Table for Grading the Severity of Adult and Pediatric Adverse Events [DAIDS AE Grading Table]). Injection-site reactions thought to be directly related to the injection are considered to be AEs of special interest, and a separate guideline for the acquisition of data related to this AE of special interest is provided in [Section 17.3](#).

For subjects who develop grade 1 event or first occurrence of grade 2 event, continue therapy as per protocol. If a subject chooses to discontinue study treatment, the site should notify the protocol team leadership, and encourage the subject to complete any remaining study visits until the toxicity resolves.

For subjects who develop grade 2 events following study drug injection, the subject should be reevaluated closely until the AE returns to Grade  $\leq 1$ , at which time study treatment may be reintroduced at the discretion of the site Investigator. If the *same* Grade 2 AE recurs following the next administration of study drug, study treatment must be permanently discontinued. Subjects experiencing Grade 3 AEs requiring permanent discontinuation of study treatment should be followed closely for resolution of the AE to Grade  $\leq 2$  and the team leadership must be notified.

Subjects with Grade 3 asymptomatic laboratory abnormalities in cholesterol, creatine kinase (CK) or triglycerides may continue study treatment.

For grade 4 events permanently discontinue therapy.

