## 4.2 TREATMENT PHASE

Treatment Phase begins with an evaluation of results of laboratory samples collected during the Screening Phase. Subjects who meet all eligibility criteria, as per data gathered from Screening Phase are to be treated. All subjects who fail to meet eligibility criteria will be considered screen failure and exit the study without further evaluation.

All subjects will continue their existing antiretroviral regimen for one week after receiving initial assigned dosing of PRO 140. Subjects will receive up to 48 weekly PRO 140 injections in the Treatment Phase, given once per week ( $\pm 3$  days) or until virologic failure, whichever occurs first. The study treatment (PRO 140 350mg or 525mg or 700mg SC injections) will be administered by a qualified medical professional (MD, DO, PA, LPN, LVN, NP, RN or CMA if permitted by state law) at clinic site or home visit or self-administered by subjects, for the duration of 48 weeks in the Treatment Phase.

As shown in [Table 4-4](#), eligible subjects will be randomized 1:1 to two treatment arms for 48 weeks.

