### 5.2 SUBJECT WITHDRAWAL

A subject who enters the Treatment Phase but does not complete the study, as defined in [Section 5.1](#), is considered to have prematurely withdrawn from the Study.

All subjects have the right to withdraw at any point during treatment without prejudice to future care. It will be documented whether or not each subject completed the clinical study. If for any subject, study treatment or observations were discontinued, the reason(s) will be recorded.

The Investigator can discontinue a subject at any time if it is considered medically necessary.

In addition, subjects WILL be withdrawn from the study, in consultation with the Medical Monitor and the Investigator, if any of the following are met:

- A subject is significantly non-compliant with the requirements of the protocol.
- The Investigator determines that it is in the best interest of the subject.
- Subject chooses to withdraw or is withdrawn due to an adverse event
- Recurring Grade 2 study drug injection related AE at two consecutive visits
- Occurrence of Grade 3 study drug injection related AE
- A subject becomes pregnant

**Note:** *The pregnancy will be followed to term for safety follow-up. Relevant safety information collected after the study has completed will be reported as supplemental information.*

- Discontinuation of study by Sponsor

Premature withdrawal from the study MAY occur if, in consultation with the Medical Monitor and the Investigator, any of the following are met:

- A subject is treated with a prohibited medication.

- Major protocol violation

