### 5.2.2 Data Collected for Withdrawn Subjects

Patients may withdraw from the study or discontinue study treatment at any time; however, CytoDyn is dedicated to minimizing missing data in this study. It is therefore suggested that all patients, regardless of whether they continue to receive study treatment, continue within the study.

Investigators considering discontinuing study treatment should contact the medical monitor prior to such discontinuation. Patients who have study treatment discontinued will continue to be followed, per protocol, whenever possible. Patients who have study treatment discontinued due to a serious adverse event will be followed until resolution or stabilization of the event.

In the event that a subject is withdrawn from the study at any time due to an adverse event or serious adverse event (SAE), the procedures stated in [Section 9.1.1](#) or [9.2.1](#), respectively must be followed.

Every attempt should be made to collect follow-up information. The reason for withdrawal from the study will be recorded in the source documents and on the appropriate page of the eCRF.

Before a subject is identified as lost-to-follow up, the site should make all reasonable efforts to contact the subject. These attempts must be documented and should include at a minimum one phone call and one certified letter.

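### Protocol Section 9.1.8 gives two incompatible instructions for a first Grade 2 injection-related event, and Sections 9.1.8 and 5.2 disagree on a recurrent one.

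*Protocol*

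**What the plan says.** Protocol Section 9.1.8 (SC Injection-related Events) has two consecutive paragraphs that both apply to a first Grade 2 event.

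- The first says: "For subjects who develop grade 1 event or first occurrence of grade 2 event, continue therapy as per protocol".
- The second says: "For subjects who develop grade 2 events following study drug injection, the subject should be reevaluated closely until the AE returns to Grade" 1 or lower, "at which time study treatment may be reintroduced at the discretion of the site Investigator". Its next sentence deals with recurrence: if the same Grade 2 event "recurs following the next administration of study drug, study treatment must be permanently discontinued".

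Protocol Section 5.2 (Subject Withdrawal) gives a list of criteria under which "subjects WILL be withdrawn from the study, in consultation with the Medical Monitor and the Investigator". One item is "Recurring Grade 2 study drug injection related AE at two consecutive visits". The list has no item for a first Grade 2 event.

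Protocol Section 5.2.2 suggests that all patients, "regardless of whether they continue to receive study treatment, continue within the study", and adds that those taken off treatment are followed where possible. Section 5.2.1, which lists the grounds for stopping study treatment, has no criterion for injection-related events.

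The SAP contains no rule that settles any of this.

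**The concern.** These are patient-safety instructions, used at up to 60 centers in an open-label trial. A site that reads the first paragraph doses through a first Grade 2 event, and a site that reads the second holds the dose. On recurrence, one section ends treatment and another ends participation.

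Several planned outputs depend on what sites do: missed administrations (SAP 3.2.1), duration of exposure and completion of 24 and 48 weeks (SAP 8.1.6), and adverse events leading to discontinuation (SAP 8.2.1.1). A subject withdrawn from the study also stops supplying follow-up data that a subject merely off treatment would supply. Injection volume rises with dose (2, 3 and 4 mL for 350, 525 and 700 mg, Protocol 6.1), and Protocol 6.2 expects some discomfort at the larger volumes. Uneven handling could therefore fall unevenly across the dose groups that the tables set side by side.

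**Working it through.** No formula or stated figure is involved. The check is to apply each instruction to the same event and see whether the action differs.

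**First Grade 2 event.** Section 4.2 states: "Subjects will receive up to 48 weekly PRO 140 injections in the Treatment Phase, given once per week", with a window of ±3 days. The next injection is therefore due 7 days after the last and is in window from day 7 − 3 = 4 to day 7 + 3 = 10.

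| Course of the event | 9.1.8, first paragraph | 9.1.8, second paragraph | Same action? |
|---|---|---|---|
| Grade 1 or lower before the next dose; investigator restarts | Dose on schedule | Dose on schedule | Yes |
| Grade 1 or lower before the next dose; investigator declines to restart | Dose on schedule | No dose | No |
| Still Grade 2 on the scheduled day, settles by day 10 | Dose on schedule | Dose delayed, possibly within window | Timing differs |
| Still Grade 2 after day 10 | Dose in window | Dose missed | No |

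Can the second paragraph be confined to later events, which would remove the conflict? No. Its opening trigger is any Grade 2 event after injection, and recurrence then gets its own sentence. The hold must therefore cover the first occurrence.

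**Recurrent Grade 2 event.**

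| | Section 9.1.8 | Section 5.2 |
|---|---|---|
| Which event | The same Grade 2 event | A recurring Grade 2 injection-related event; sameness not stated |
| When | After the next administration | At two consecutive visits |
| Consequence | Permanent end of study treatment | Withdrawal from the study |

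The triggers can separate. Suppose a dose is held at one weekly visit, the next is given a week later, and the same event returns. The 9.1.8 condition is met, but the two occurrences need not fall at consecutive visits. Conversely, two different Grade 2 injection reactions at consecutive visits could meet 5.2 and not 9.1.8. The consequences differ even when both triggers are met, and the 5.2 consequence runs against the follow-up intended in 5.2.2.

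**Exit route.** Section 4.2 ties the end-of-treatment assessments, entry to follow-up and restart of antiretroviral therapy to the criteria in 5.2.1, and Section 7.5.1 does the same for the restart. Since 5.2.1 omits injection-related events, a subject stopped only under 9.1.8 has no explicit route unless the subject or clinician asks to restart antiretroviral therapy, which 5.2.1 does list.

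**The case against.** The strongest reply is that no sentence in 9.1.8 orders a hold; it is inferred from the word for restarting treatment. Many Grade 2 reactions may settle within a week, in which case both paragraphs usually lead to the same dose on the same day. Section 9.1.8 also mixes general toxicity rules with injection rules, so the first paragraph might be read as general and the second as specific. On recurrence, weekly dosing makes the two triggers nearly coincide, and a recurring event may naturally mean the same event. The SAP plans no inferential statistics (7.3 and 7.4), and Protocol 9.1.2 already records whether an adverse event interrupted treatment.

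Much of this stands, and it limits the point. The conflict is conditional, and the data needed to see it are largely collected. It does not remove the point. A return to treatment makes no sense without an interruption, and a first Grade 2 injection reaction meets both triggers under a heading that concerns injection events. On recurrence, the difference between leaving treatment and leaving the study remains however the trigger is read.

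A reader might infer three stronger things that the documents do not support.

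- *That 5.2 also conflicts on a first Grade 2 event.* It says nothing about one.
- *That every hold costs at least one weekly dose.* An event may settle before the next dose or within its window, and no durations are given.
- *That holds lead to virologic failure.* Other antiretrovirals are barred during monotherapy outside listed exceptions (7.5.1), and Section 1.4.2.4 gives half-lives of 3.5 to 3.9 days after single intravenous doses. Assuming first-order elimination, an extra 7 days is 7/3.9 = 1.8 to 7/3.5 = 2.0 half-lives, leaving about 29% to 25% of the usual trough. However, Section 1.3 reports concentrations above the IC50 for at least two weeks after a single 324 mg dose, and Section 1.4.2.6 reports no rebound between 324 mg doses in a study with an every-other-week arm. An effect is possible, not shown.

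**Conclusion.** The point holds in two parts. Section 9.1.8 contradicts itself on a first Grade 2 injection-related event, with a practical difference when Grade 2 persists to the next weekly dose or the investigator declines to restart. Separately, 9.1.8 and 5.2 differ in trigger and consequence for a recurrent Grade 2 event, and 5.2 sits badly with 5.2.2.

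The effect on missed doses, exposure and discontinuation counts cannot be sized, because the documents give neither a frequency nor a duration for Grade 2 injection events. The conclusion rests on wording alone, on the assumption that reintroducing treatment presupposes a hold. Because the analysis is descriptive, no test or error rate is affected. The correction should be made because sites need one safety instruction and because the by-dose tolerability tables depend on it.

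**What to change.** Reconcile the two paragraphs of 9.1.8 with each other, and 9.1.8 with 5.2, 5.2.1 and 5.2.2, so that:

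- one instruction covers a first Grade 2 injection-related event;
- one covers recurrence, stating whether it must be the same event and how the interval is counted (administrations or visits);
- one states whether the subject leaves treatment or the study, and which end-of-treatment and follow-up visits apply.

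Which clinical rule applies is for the sponsor and its clinical advisers.

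In the SAP, add a table by dose group of adverse events whose recorded impact was an interruption of study treatment, next to the planned summary of those leading to discontinuation. Protocol 9.1.2 already collects this.

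The cost is a protocol clarification, a note to sites and one descriptive table. No new data are needed.
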